| 16.8. | Publication and Use of Information..... | 44 |
| 16.9. | Suspension or Early Termination | 45 |
| 17. | References | 46 |
| 18. | Version History..... | 48 |

2. Glossary

| Term | Definition |
|------|---|
| ADE | Adverse Device Effect |
| AE | Adverse Event |
| AF | Atrial Fibrillation |
| AFCL | Atrial Fibrillation Cycle Length |
| ATP | Anti-tachycardia Pacing |
| BP | Blood Pressure |
| CE | Conformity European |
| CIP | Clinical Investigation Plan |
| CRF | Case Report Form |
| CS | Coronary Sinus |
| CTA | Clinical Trial Agreement |
| CV | Curriculum Vitae |
| DD | Device Deficiency |
| DTL | Delegated Task List |
| EC | Ethic Committee |
| ECG | Electrocardiogram |
| EP | Electrophysiology Procedure |
| ICF | Informed Consent Form |
| ISF | Investigator Site File |
| LA | Left Atrium |

AF Septal Pacing Clinical Investigation Plan

Version 3.0 22-Nov-2017

Page 7 of 49

Medtronic

| Term | Definition |
|--------------------|--|
| PCL | Pacing Cycle Length |
| PV | Pulmonary Vein |
| RA | Right Atrium |
| SADE | Serious Adverse Device Effect |
| SAE | Serious Adverse Event |
| USADE | Unanticipated Serious Adverse Device Effect |

3. Synopsis

| Title | AF Septal pacing | | | |
|---|--|-------------------|---|--|
| Clinical Study Type | Non-randomized, non-controlled, acute, single-arm research study | | | |
| Product Name | PV ablation system | | | |
| Sponsor | Medtronic Bakken Research Center B.V. [name] The Netherlands | | | |
| Indication under investigation | Subjects suffering of either persistent and paroxysmal Atrial Fibrillation, indicated for ablation of the pulmonary vein. | | | |
| Investigation Purpose | To evaluate the feasibility to obtain a stable position of a ring of stimulation electrodes on the interatrial septum. | | | |
| Product Status | All devices used in this clinical study are CE marked and used within the approved indications in the participating countries. The devices and accessory components that might be used in the study are listed in the below table 1: | | | |
| Table 1: Devices and accessory components used in AF Septal Pacing | | | | |
| Component and Model name | Comments | Regulatory Status | Intended Use | Investigational |
| Decapolar Lasso catheter (Biosense Webster, model number Lasso 2515 NAV) | Preferably the Lasso Biosense Webster catheter, since it was used in acute animal studies and positive results were obtained. Positive results were not obtained with the PVAC and MASC catheter. | CE marked | Indicated for multiple electrode electrophysiological mapping of the cardiac structures of the heart, i.e. recording or stimulation only. The catheter is designed to obtain electrograms in the atrial regions of the heart. | NO (CE marked used within approved indications) |

AF Septal Pacing Clinical Investigation Plan

Version 3.0 22-Nov-2017

Page 9 of 49

Medtronic

| | | | | |
|---|---|-----------|--|--|
| | | | (one per subject) | |
| Achieve catheter (Medtronic Inc) (single use) (model 990063-020) | In case no stable position can be obtained with the Lasso catheter, we will use the Achieve catheter from Medtronic. | CE marked | Indicated as an intra-cardiac electrophysiology (EP) recording catheter and can be used for cardiac stimulation during electrophysiology studies. (one per subject) | NO (CE marked used within approved indications) |
| EP4 stimulator (St Jude, Minneapolis, USA, model number H403023) | Or any other four channel electrophysiological stimulator standard used in the EP lab of the hospital. | CE marked | Indicated as a cardiac stimulator. (one per site) | NO (CE marked used within approved indications) |
| Monitoring catheters: two decapolar mapping electrodes | Any decapolar routinely used in the hospital to monitor signals in right atrium and coronary sinus. | CE marked | Monitoring (one per subject) | NO (CE marked used within approved indications) |
| Monitoring system. | Could be e.g. a stationary Bard EP recording system, a physiological recorder, such as the porti-system (TMSI) or any other electrophysiological monitoring system used in EP lab | CE marked | Monitoring (one per site) | NO (CE marked used within approved indications) |

AF Septal Pacing Clinical Investigation Plan

Version 3.0 22-Nov-2017

Page 10 of 49

Medtronic

| | | | | | |
|---|--|--------------------------------|--|--|--|
| | | during the ablation procedure. | | | |
| Primary Objective | To evaluate the feasibility to obtain a stable position of a ring of stimulation electrodes on the interatrial septum. | | | | |
| Secondary Objectives | 
• Localized Atrial Capture: evaluate if during the rapid pacing phase of the dual-stage septal pacing scheme (rapid pacing followed by a step-wise transition to slow-pacing) from multiple electrodes on the interatrial septum, local atrial capture can be observed during atrial fibrillation.• AF Termination Scheme: evaluate if AF termination can be obtained using a dual-stage septal pacing scheme (rapid pacing followed by a step-wise transition to slow-pacing) from multiple electrodes on the interatrial septum. | | | | |
| Study Design | Approximately 15 subjects with AF indicated for ablation of the pulmonary vein will be enrolled in the study. Participants will attend the Baseline visit and the Procedure visit. The baseline visit can be on the same day as the ablation procedure. Since it is an acute study, no follow-up visit will occur. The research procedure will be performed during an already scheduled ablation procedure. Subjects will be enrolled over a period of approximately 18 months | | | | |
| Sample Size | Approximately 15 subjects suffering of either persistent and paroxysmal Atrial Fibrillation, indicated for ablation of the pulmonary vein will be enrolled in the study. No control group will be used for this study. The study is planned to be conducted at up to 3 centers in Europe. | | | | |
| Inclusion/Exclusion Criteria | 
All of below inclusion criteria must be met:
 
• Patient referred to the center to undergo ablation of the pulmonary vein using radiofrequency (initial AF ablation, or redo procedure).• In case of paroxysmal, AF the right atrium should be dilated as indicated by $> 29 \text{ ml mm}^2$ or the left atrium should be dilated as indicated by $> 34 \text{ ml mm}^2$.• Patient is willing and able to cooperate with the study procedure.• Patient is willing to provide the Informed Consent for their participation in the study. 
None of the below exclusion criteria must be met:
 
• Patients under 18 years or over 80 years old.• Women who are currently pregnant or have a positive pregnancy test.• Patients with an implantable cardiac device.• Patients who already underwent an AF septal ablation procedure. | | | | |
| Study Procedures and Assessments | 
Baseline: Patients will be pre-screened for potential enrolment in the clinical investigation by evaluating if the patients meet the inclusion and exclusion criteria. Next the patient is asked for her or his informed consent. A patient is considered an enrolled subject after he/she has personally signed and dated the ICF. At baseline, subject characteristics will be noted such as age, gender, weight, height, AF status and AF history.
 | | | | |

Enrolled subjects will undergo the AF ablation procedure, for which they have been referred to the center. For this standard procedure, the subject will be prepared as per standard catheterization/EP procedures, which includes administration of anesthesia/analgesia, ECG and BP monitoring.

Procedure:

The subject will be sedated. A trans-septal puncture will be made to access the left atrium and place a septal catheter and the clinically used ablation catheter. One decapolar recording catheter will be placed in the right atrium and one decapolar recording catheter will be placed in the coronary sinus. Both decapolar catheters are used according to standard clinical practice. The standard procedure workflow is visualized on the left side of figure 1 below.

After successful pulmonary vein isolation, there is a routine waiting time of half an hour to confirm efficacy of the ablation procedure. During this waiting period, the study procedure will be performed. The deviations from the standard procedure are indicated in orange on the right of figure 1 below. The septal catheter, already in place in the right atrium, will be positioned on the left interatrial septum via a trans-septal approach. In most cases the patient will be in sinus rhythm.

During sinus rhythm pacing thresholds and impedances on all septal catheter electrodes will be determined. Also, potential ventricular capture will be assessed.

Next, atrial fibrillation will be induced by rapid atrial pacing. AF cycle length will be determined, during 1 minute of atrial fibrillation using the ablation catheter electrodes. Subsequently, the rapid phase of the two-stage atrial pacing scheme will be applied to four septal electrodes at same time during half a minute using the quadripolar electrophysiological stimulator (e.g. EP4 stimulator). An electrophysiological recording system (already in place for the AF ablation procedure), recording all atrial electrograms, will be used to assess the study outcome of local atrial capture. In addition, if feasible, AF termination will be evaluated using the two-stage pacing algorithm. If needed cardioversion will be used to terminate AF.

In a minority of cases the subject will still be in AF after successful pulmonary vein isolation. In these cases, the ventricular capture tests as described above will be performed first, then AF cycle length will be determined, and the rapid phase of the two-stage atrial pacing scheme as described above will be performed. If delivery of the two-stage atrial pacing scheme either will not be feasible or not stop the AF, the subject will be externally cardioverted under deep sedation as would have been done as common practice at the end of the ablation procedure. Next, during sinus rhythm pacing thresholds and impedances on all septal catheter electrodes will be determined.

Protocol deviations from what is stated above will be documented.

[figure not shown]
Figure 1: Study steps to be added to standard procedure.

AF Septal Pacing Clinical Investigation Plan

Version 3.0 22-Nov-2017

Page 12 of 49

Medtronic

4. Introduction

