After successful pulmonary vein isolation, there is a routine waiting time of half an hour to confirm efficacy of the ablation procedure. During this waiting period, the study procedure will be performed. The deviations from the standard procedure are indicated in orange on the right of figure 1 below. The septal catheter, already in place in the right atrium, will be positioned on the left interatrial septum via a trans-septal approach. In most cases the patient will be in sinus rhythm. In these cases, during sinus rhythm pacing thresholds and impedances on all septal catheter electrodes will be determined. Also, potential ventricular capture will be assessed. Next, atrial fibrillation will be induced by rapid atrial pacing. AF cycle length will be determined, during 1 minute of atrial fibrillation using the ablation catheter electrodes. Subsequently, the rapid pacing phase of the two-stage atrial pacing scheme will be applied to four septal electrodes at same time during half a minute using the quadripolar electrophysiological stimulator (e.g. EP4 stimulator). An electrophysiological recording system (already in place for the AF ablation procedure), recording all atrial electrograms, will be used to assess the study

[figure not shown]
outcome of local atrial capture. In addition, if feasible, AF termination will be evaluated using the two-stage pacing algorithm. If needed cardioversion will be used to terminate AF.

In a minority of cases the subject will still be in AF after successful pulmonary vein isolation. In these cases, the ventricular capture tests as described above will be performed first, then AF cycle length will be determined, and the two-stage atrial pacing scheme as described above will be performed. If delivery of the slow pacing phase of the two-stage atrial pacing scheme either will not be feasible or not stop the AF, the subject will be externally cardioverted under deep sedation as would have been done as common practice at the end of the ablation procedure. Next, during sinus rhythm pacing thresholds and impedances on all septal catheter electrodes will be determined.

[figure not shown]
Protocol deviations from what is stated above will be documented.

Figure 1: Study steps to be added to standard procedure.

STANDARD ABLATION PROCEDURE

AF SEPTAL PACING STUDY DURING STANDARD ABLATION PROCEDURE

*Patient is under deep sedation for whole procedure
§ If subject is still on AF

No follow-up data will be requested for the study.

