Next, atrial fibrillation will be induced by rapid atrial pacing, gradually elevating the atrial pacing rate until 1:1 atrial capture is lost. AF cycle length will be determined by recording the atrial electrogram on the septum. Stimulation on the septum from all electrodes starts at the current defined above, using various pacing cycle length (PCL), being percentages of AFCL and will last for 10 to 30 seconds, depending on when capture occurs, followed, if feasible, by slow pacing using an interval of 130% of AF for one cycle followed by 1.5 second of 180% of AF Cycle length at maximum output which did not induce ventricular capture (20 mA or lower). Multiple PCLs will be used to start the pacing sequence. During each stimulation sequence, corresponding to each PCL, atrial capture at each recording electrode will be assessed. The optimal parameters for stimulation will be used to determine local capture for all electrodes.

When the subject will still be in AF after successful pulmonary vein isolation the ventricular capture tests will be performed first during atrial fibrillation (as described above for subject in sinus rhythm). Then, AF cycle length will be determined and

the two-stage atrial pacing scheme as described above will be performed. If delivery of the two-stage atrial pacing scheme either will not be feasible or not stop the AF, the subject will be externally cardioverted under deep sedation as would have been done as common practice at the end of the ablation procedure. Next, during sinus rhythm pacing thresholds and impedances on all septal catheter electrodes will be determined.

To assess if the two-stage pacing scheme can terminate AF, the surface ECG will be analyzed and PCL and stimulation current will be noted.

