AF Termination Scheme: evaluate if AF termination was observed during the experimental atrial septal pacing scheme from multiple electrodes on the interatrial septum. Acute procedural AF termination was defined as termination of AF to SR or a regular atrial tachycardia/flutter during the experimental pacing procedure without re-initiation of atrial fibrillation during the experimental pacing scheme.

AF termination will be described as the count and frequency of any AF termination
Subgroup descriptions and summary of atrial capture and AF termination will be done for:

- Atrial fibrillation group (SR vs AF group)
- Catheter type (Achieve vs. Lasso or other)
- Anatomical electrode position
- Atrial Cycle Length

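### For subjects still in AF, the protocol passages disagree on the pacing given before cardioversion, and the SAP counts termination without regard to stage, so the count is not a result for the dual-stage scheme

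*Protocol*

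**What the plan says.** Three protocol passages describe the subject who is still in AF after successful isolation.

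- **Synopsis (Section 3, Study Procedures).** After the ventricular capture tests and the AF cycle length, "the rapid phase of the two-stage atrial pacing scheme as described above will be performed". The next sentence reads "If delivery of the two-stage atrial pacing scheme either will not be feasible or not stop the AF, the subject will be externally cardioverted". The preceding paragraph, on subjects in sinus rhythm, adds: "In addition, if feasible, AF termination will be evaluated using the two-stage pacing algorithm".
- **Section 10, Study Procedures.** The corresponding text is "and the two-stage atrial pacing scheme as described above will be performed", and the cardioversion sentence begins "If delivery of the slow pacing phase of the two-stage atrial pacing scheme either will not be feasible or not stop the AF".
- **Section 10.3, Assessment of Efficacy.** The two-stage scheme is performed, and the cardioversion sentence begins "If delivery of the two-stage atrial pacing scheme either will not be feasible or not stop the AF". The scheme it refers back to has 10 to 30 seconds of rapid pacing, then slow pacing if feasible, and "Multiple PCLs will be used to start the pacing sequence".

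The termination objective (protocol synopsis and 5.1.2, SAP 5.2) concerns the dual-stage scheme, that is, rapid pacing followed by the transition to slow pacing. SAP 8.7.2 defines termination as conversion to sinus rhythm or a regular atrial tachycardia or flutter during the experimental pacing. It summarises the count and frequency of any such event and lists subgroup descriptions, among them "Atrial fibrillation group (SR vs AF group".

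**The concern.** A site that takes the synopsis sentence at its word may deliver rapid pacing and go on to cardioversion. A site that works from Section 10 or 10.3 will attempt the slow phase first. Up to three centres take part, so practice could differ between them, and an omitted slow phase could not be classed consistently as a deviation.

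The stage matters on the protocol's own account. Section 4.1 reports that animal and human mapping experiments did not see AF terminate with rapid pacing alone, and that rapid septal pacing in the computer model generally did not terminate it either. The second stage was developed on that basis. A subject who receives only the rapid phase therefore does not test the dual-stage objective. If the analysis does not separate such subjects from those who received both stages, the termination frequency mixes two interventions.

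**Working it through.** The plan gives no figure to reproduce: both documents state that there is no hypothesis test and no sample size calculation. The check sets the texts side by side, then follows the objective into the SAP.

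**1. Subjects still in AF, by passage**

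| Item | Synopsis | Section 10 | Section 10.3 |
|---|---|---|---|
| Stages named | Rapid phase | Both stages | Both stages |
| Cardioversion follows if | Two-stage scheme infeasible or AF not stopped | Slow phase infeasible or AF not stopped | Same as synopsis |
| Rapid-phase duration | Half a minute | Half a minute | 10 to 30 s, depending on capture |
| Cycle lengths | Not stated | Not stated | Multiple |
| Thresholds and impedances | In sinus rhythm, after the cardioversion step | Same | Same |

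The first four rows do not agree across the passages. The last row does.

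**2. From objective to analysis**

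- The objective is dual-stage wherever it is stated.
- Delivery of the slow phase is conditional on feasibility, for subjects in induced AF as well as those still in AF.
- SAP 8.7.2 counts any termination during the experimental scheme. An event in the rapid phase and an event after both stages count alike, and no denominator of subjects who received both stages is given.
- SAP Tables 5 and 6 both name AF termination in their titles. Their fields cover electrode configuration, experiment number, AF cycle length, paced interval, rhythm group, stimulation mode and output, and capture. Neither table lists a field for slow phase delivered or for termination.

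**3. Scale**

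- Length of the slow stage = 1.3 × AFCL + 1.5 s. The SAP field range for AFCL is 100 to 400, taken here as ms. This gives 1.3 × 0.100 + 1.5 = 1.63 s to 1.3 × 0.400 + 1.5 = 2.02 s.
- One sequence is therefore 30 s if rapid only for half a minute, 31.63 to 32.02 s if both stages follow a half-minute rapid phase, and 11.63 to 32.02 s under Section 10.3 for each cycle length used. The slow stage adds about two seconds, so what is at stake is which intervention was given rather than procedure time.
- One subject of 15 is 100/15 = 6.7 percentage points.
- Illustration only: let k subjects be still in AF and let p be the chance that the slow stage ends AF in such a subject. The chance that leaving it out changes at least one result is 1 − (1 − p)^k. Neither k nor p is given. For k = 1 to 7 (an assumed reading of a minority of 15), this is 5% to 30% at p = 0.05 and 29% to 91% at p = 0.29. The 0.29 is the computer model's best figure for the whole scheme at its optimal cycle length, so it is an upper illustrative value.

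**The case against.** The strongest reply is that this is loose drafting in a synopsis. Its cardioversion sentence presupposes the two-stage scheme, its preceding paragraph evaluates termination with the two-stage algorithm, and it shares its cardioversion wording with Section 10.3. Thirty seconds lies within 10 to 30 seconds. The study is descriptive, and SAP 8.4 plans no statistical comparison between groups. The surface ECG and electrograms are recorded, so stage and outcome might be recovered afterwards, and the case report form itself is not among the documents.

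Much of this stands, and it rules out several stronger readings that a reader might infer:

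- *That the synopsis is rapid-only, so nobody still in AF tests the objective.* Its next sentence contradicts this. The synopsis is internally inconsistent.
- *That Section 10 would cardiovert a subject whose AF stopped during rapid pacing.* This is strained. Section 10 speaks of cardioversion if needed to end AF, and all three passages cardiovert when AF persists.
- *That the slow phase is conditional for induced AF but mandatory for those still in AF.* The back-reference to the scheme described above carries the feasibility condition over, and the next sentence provides for infeasibility.
- *That the passages set one run against a series, with a calculable gap in the share cardioverted.* No passage says there is a single run, and the number of cycle lengths is not given. Any such gap would rest on assumed run counts and would not measure the stage mismatch.
- *That the primary endpoint is affected.* The order of threshold measurement for these subjects is the same in all three passages.

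What the reply does not remove is the disagreement on the stages named and on the wording before cardioversion, or the absence of a stage-specific count in the SAP. Possible recovery from recordings is no substitute for a planned variable and denominator.

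**Conclusion.** The point holds in limited form. For subjects still in AF, three current passages do not give one account of the pacing that precedes cardioversion. Separately, and for all subjects, the SAP's termination count takes no account of whether the slow phase was delivered, so it cannot be read as a result for the dual-stage scheme.

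The size is modest. The conflict between passages touches only a minority of about 15 subjects, whose number the documents do not give. The outcome is a descriptive secondary endpoint. How many results would change cannot be calculated from the documents; the illustrative range above depends wholly on assumed k and p. The conclusion about data fields rests on the SAP table descriptions, since the case report form was not available. Correction is worthwhile because it is cheap and because the stated objective cannot otherwise be answered cleanly.

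**What to change.** **Protocol.** Reconcile the synopsis, Section 10 and Section 10.3 into one sequence for subjects still in AF: which stages are delivered, how many runs and for how long, and which event precedes cardioversion. Which version is right is for the sponsor to decide.

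**SAP 8.7.2.** Report termination by stage delivered (rapid phase only versus both stages), overall and within the SR and AF groups. State how many subjects received both stages and use that number as the denominator for the dual-stage objective. Add two fields to the experiment-level table (Table 5): slow phase delivered, and termination result.

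A comparison restricted to each subject's first run is not needed and would not be clearly comparable, because no first cycle length is fixed.

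**Cost.** Wording in three protocol passages, a short addition to SAP 8.7.2, two data fields and one extra descriptive table. With so few subjects the cells will be small, so counts should be shown beside any percentages.
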